6.1.4. Prior Therapy

The number of prior systemic regimens for MF other than ruxolitinib will be summarized for all participants in the ITT population by treatment group. The component drugs of prior systemic therapy regimens will be coded using the WHO Drug Dictionary. The number and percentage of participants who received each drug will be summarized by WHO drug class and WHO drug PT. The regimen name, route, dose, frequency, start and stop dates, and reason for discontinuation will be listed.

The number of participants who received prior radiation for non-MF-related cancer treatment will be summarized for the ITT population by treatment group. The radiotherapy type, body site, start and stop dates, reason for regimen, total dose, number of fractions received, and best response will be listed.

The number of participants who had prior surgery or a surgical procedure for non-MF-related cancer treatment will be summarized for the ITT population by treatment group. The date and description of the surgery/procedure will be listed.

6.1.5. Medical History

For participants in the ITT population, medical history will be summarized by assigned treatment group. This summation will include the number and percentage of participants with significant medical history for each body system/organ class as documented on the eCRF.

6.1.6. Ruxolitinib History

The duration and total daily dose of ruxolitinib treatment prior to Day 1, as well as the duration and total daily dose of stable ruxolitinib treatment prior to Day 1 will be summarized for the ITT population by treatment group.

6.2. Disposition of Participant

The number and percentage of participants who were randomized, who were treated, who were ongoing with study treatment, who discontinued study treatment with a primary reason for discontinuation, who were still in the study, and who withdrew from the study with a primary reason for withdrawal will be summarized for the ITT population by treatment group. The number of participants randomized by country and/or site will also be provided by treatment group.

6.3. Protocol Deviations

Protocol deviations recorded in the clinical trial management system will be summarized and listed.

6.4. Exposure

For participants in the safety population, exposure to parsaclisib/placebo and ruxolitinib will be summarized descriptively as the following:

- **Duration of treatment with ruxolitinib (days):** date of last dose of ruxolitinib – date of first dose of ruxolitinib + 1.
- **Duration of treatment with parsaclisib/placebo (days):** date of last dose of parsaclisib/placebo – date of first dose of parsaclisib/placebo + 1.
- **Average daily dose of ruxolitinib (mg/day):** total actual ruxolitinib dose taken (mg) / duration of treatment with ruxolitinib (days).
- **Average daily dose of parsaclisib/placebo (mg/day):** total actual parsaclisib/placebo dose taken (mg) / duration of treatment with parsaclisib/placebo (days).

Total actual dose taken will be calculated based on the information entered on the Drug Exposure eCRF.

- **Total dose administered for ruxolitinib (mg):** sum of ruxolitinib administered (mg) during treatment.
- **Total dose administered for parsaclisib/placebo (mg):** sum of parsaclisib/placebo administered (mg) during treatment.

6.5. Study Drug Compliance

For participants in the safety population, overall compliance (%) for parsaclisib/placebo will be calculated for all participants as follows:

$$\text{compliance (\%)} = 100 \times [\text{total dose actually taken}] / [\text{total prescribed dose}].$$

The total prescribed dose is defined as the sum of the doses prescribed by the investigator accounting for dose modifications.

The total actual dose taken will be calculated based on information entered on the Drug Accountability eCRF. If there are dispensed drugs that have not been returned yet, the actual dose taken starting from the dispense date of the unreturned drugs will be imputed by the dose taken as reported on the Dosing eCRF.

6.6. Prior and Concomitant Medication

Prior medications and concomitant medications will be coded using the WHO Drug Dictionary. The number and percentage of participants in the ITT population for each prior and concomitant medication will be summarized by WHO drug class and WHO drug PT for each treatment group.

7. EFFICACY

[Appendix A](#) provides a list of data displays. Sample data displays are included in a separate document.

7.1. General Considerations

Unless otherwise stated, the strata identified in the randomization process will be used in all efficacy analyses. Within a platelet category, in the event that the study fails to enroll a sufficient number of participants in a particular DIPSS stratification level, at the time of final analysis for database lock, that stratification will be combined with the nearest adjacent DIPSS level (eg, intermediate-1 vs intermediate-2 vs high). For example, if either intermediate-1 or high-risk is too small (eg, fewer than 10 participants), it will be merged with intermediate-2. If intermediate-2 has too few participants (eg, fewer than 10 participants), then it will be merged with the smaller of the 2 adjacent strata. At the time of interim analyses, all DIPSS stratification levels will be combined if too few participants (eg, fewer than 10 participants) are enrolled in 1 DIPSS stratification level.

The ITT population will be used for all efficacy analyses unless otherwise stated.

7.2. Efficacy Hypotheses

The primary hypothesis is that the percentage of participants achieving $\geq 25\%$ reduction in spleen volume from baseline to Week 24 in the parsaclisib plus ruxolitinib treatment group will not be the same as the percentage of participants achieving $\geq 25\%$ reduction in spleen volume from baseline to Week 24 in the placebo plus ruxolitinib treatment group as measured by the odds ratio. The hypotheses of the study are as follows:

- H_0 (null hypothesis): $\theta_{PAR} = \theta_{PLB}$
- H_A (alternative hypothesis): $\theta_{PAR} \neq \theta_{PLB}$

7.3. Analysis of the Primary Efficacy Endpoint

7.3.1. Primary Efficacy Analysis

The primary endpoint of this study is the proportion of participants with $\geq 25\%$ spleen volume reduction from baseline to Week 24 as measured by MRI (or CT scan in applicable participants). The primary endpoint will be analyzed by the CMH test stratified by DIPSS risk category (intermediate-1 vs intermediate-2 vs high) and baseline (or screening, if applicable) platelet count ($\geq 100 \times 10^9/L$ vs 50 to $< 100 \times 10^9/L$ inclusive).

The baseline spleen volume will be measured during the baseline visit (Days -7 to 1); the last value will be used if there are multiple values measured during the baseline visit.

The Week 24 spleen volume will be measured during the Week 24 visit; the last value will be used if there are multiple values measured during the Week 24 visit. Missing values will not be imputed.

The percentage change from baseline to Week 24 will be calculated using the following formula:

$$\% \text{ change} = 100 \times [\text{Week 24 spleen volume} - \text{baseline spleen volume}] / \text{baseline spleen volume.}$$

A participant will be considered as having achieved $\geq 25\%$ reduction of spleen volume from baseline to Week 24 if the participant had both baseline and Week 24 spleen volume measurements, the participant did not make an early crossover to receive parsaclisib plus ruxolitinib prior to the Week 24 visit, and the percentage change from baseline reduction was $\geq 25\%$.

A participant who has a missing Week 24 spleen volume, discontinues treatment before Week 24, or makes an early crossover to receive parsaclisib plus ruxolitinib prior to the Week 24 visit will be considered as a nonresponder for the endpoint of $\geq 25\%$ reduction of spleen volume.

A participant who has a missing baseline assessment will be considered as nonevaluable.

At the time of interim analysis, a participant who is still on treatment, but has not followed up for the timepoint assessment and has no timepoint assessment, will also be considered as nonevaluable.

7.3.2. Subgroup Analyses for Primary Endpoint

Subgroups will be formed based on the following participant characteristics and baseline variables for those participants whose data are available. If the number of participants is too small (eg, 10 participants) in a subgroup, then the analysis will not be conducted in that subgroup.

- Baseline platelet count: $\geq 100 \times 10^9/\text{L}$ versus $50 \text{ to } < 100 \times 10^9/\text{L}$ inclusive. Note that if a participant's platelet count is $< 50 \times 10^9/\text{L}$ at baseline, the platelet count at screening will be used for stratification/randomization.
- DIPSS risk category: high versus intermediate-2 versus intermediate-1
- Sex: male versus female
- Age group: ≤ 65 years or > 65 years
- MF type: PMF, PPV-MF, or PET-MF
- Ruxolitinib average total daily dose during the 8 weeks before randomization: $< 20 \text{ mg}$, $20 \text{ to } 30 \text{ mg}$ inclusive, or $> 30 \text{ mg}$
- Overall duration of treatment with ruxolitinib before randomization: $\leq \text{median}$ or $> \text{median}$
- Presence/absence of V617F mutation at baseline
- Presence/absence of HMR mutations at baseline
- Baseline spleen volume group: $\leq \text{median}$ or $> \text{median}$
- Baseline spleen palpation size group: $\leq 10 \text{ cm}$ or $> 10 \text{ cm}$
- Race: White/Caucasian, Black/African-American, Asian, American-Indian/Alaska Native, Native Hawaiian/Pacific Islander, or other
- Ethnicity: Hispanic/Latino, not Hispanic/Latino, or other

A forest plot with odds ratio and 95% CI for the primary endpoint subgroup analyses will be provided.

7.3.3. Sensitivity and Supportive Analyses for Primary Endpoint

The primary endpoint will be analyzed using the PP population as a supportive analysis to the ITT population.

The participants who make an early crossover and later turn into responders will be considered as responders and analyzed in the placebo group as a supportive analysis.

In the event that 2 DIPSS stratification levels are combined, a sensitivity analysis for the primary endpoint without combining levels will be conducted.

Due to early study termination, sensitivity and supportive analyses will not be performed.

7.4. Analysis of the Secondary Efficacy Parameters

7.4.1. Spleen Volume Reduction

7.4.1.1. Time to the First $\geq 25\%$ Reduction in Spleen Volume

The time to the first $\geq 25\%$ reduction in spleen volume is defined as the time from randomization to the first time participants have a $\geq 25\%$ reduction in spleen volume. Participants with baseline and postbaseline MRI or CT scan who do not have a $\geq 25\%$ reduction in spleen volume at the time of analysis will be censored at the time of the last MRI or CT scan. If the participants have no baseline or postbaseline MRI or CT scan, they will be censored at the date of randomization.

The stratified log-rank test will be used to compare the time to the first $\geq 25\%$ reduction in spleen volume between the 2 treatment groups in the ITT population at a 1-sided 2.5% significance level, stratified for baseline (or screening, if applicable) platelet count and DIPSS category. The strata identified in the randomization process will be used for the analysis.

Kaplan-Meier curves for the time to the first $\geq 25\%$ reduction in spleen volume will be presented by treatment group. The KM estimate of median time to the first $\geq 25\%$ reduction in spleen volume will be presented with its 95% CI. The 95% CI will be calculated using the generalization of method of Brookmeyer and Crowley (1982) with log-log transformation (Klein and Moeschberger 1997).

Since only a limited number of $\geq 25\%$ reduction in spleen volume response was observed at the time of study termination, time to the first 25% reduction in spleen volume will not be performed.

7.4.1.2. Duration of Maintenance of a $\geq 25\%$ Reduction in Spleen Volume

The duration of a $\geq 25\%$ reduction from baseline in spleen volume is defined as the interval between the first spleen volume measurement that is $\geq 25\%$ reduction from baseline and the date of the first measurement that is no longer a $\geq 25\%$ reduction from baseline. If the end date is not observed before the database cutoff, the duration will be censored at the last assessment.

The endpoint will be derived for participants who were randomized and who had at least 1 measurement of $\geq 25\%$ reduction from baseline.

Kaplan-Meier estimates of median duration with 95% CIs will be provided.

The ITT population with spleen volume response will be used.

A supportive analysis for the duration of a $\geq 25\%$ reduction from baseline in spleen volume defined as the interval between the first spleen volume measurement that is $\geq 25\%$ reduction from baseline and the date of the first measurement that is no longer a $\geq 25\%$ reduction from baseline that is also a $> 25\%$ increase from nadir will be provided.

At the time of study termination, only a limited number of $\geq 25\%$ reduction in spleen volume response was observed; therefore, duration of a 25% reduction in spleen volume will not be performed.

7.4.2. Myelofibrosis Symptom Assessment Form Total Symptom Score v4.0

The MFSAF v4.0 is composed of 7 individual symptom scores (fatigue, night sweats, itchiness, abdominal discomfort, pain under left ribs, early satiety, and bone pain), each collected daily with a 0- to 10-point scale.

The daily MFSAF TSS is the sum of the 7 individual symptom scores collected on the same day. The MFSAF TSS will be missing if there are any missing individual scores. Observations with missing dates will be excluded from the analysis.

The baseline total score is defined as the average of daily total scores from the last 7 days before the first dose of parsaclisib/placebo; the baseline total score will be missing if there are ≥ 4 missing out of the 7 daily total scores.

The Week 12 total score will be the average of daily total scores from the first 7 consecutive days starting on Day 78; the Week 12 total score will be missing if there are ≥ 4 missing out of the 7 daily total scores.

The Week 24 total score will be the average of daily total scores from the 7 consecutive days before the Week 24 visit; the Week 24 total score will be missing if there are ≥ 4 missing out of the 7 daily total scores.

The percentage change from baseline to Week 12/Week 24 will be calculated using the following formula:

$$\% \text{ change} = 100 \times [\text{Week 12/Week 24 MFSAF TSS} - \text{baseline MFSAF TSS}] / \text{baseline MFSAF TSS}.$$

7.4.2.1. Windowing of Myelofibrosis Symptom Assessment Form v4.0 Total Symptom Score

7.4.2.1.1. Myelofibrosis Symptom Assessment Form v4.0 Total Symptom Score for Non-Time-to-Event Endpoints

The MFSAF v4.0 TSS for baseline, Week 12, and Week 24 will be determined by averaging the daily MFSAF v4.0 TSS for the days between the start and end of windows as described in [Table 3](#). By-question summaries for the 7 individual symptom scores that compose the MFSAF TSS at baseline, Week 12, and Week 24 will use the same windowing algorithm as used for the daily TSS.

The TSS and the 7 individual scores at Weeks 4, 8, 16, and 20 will be derived in a similar fashion using the first nonmissing daily TSS available between

Day $(7 \times \text{Week X} - 6)$ and Day $(7 \times \text{Week X})$

as the start of the window.

Table 3: Window for Deriving Myelofibrosis Symptom Assessment Form v4.0 Total Symptom Score for Baseline, Week 12, and Week 24

Period	Start of Window	End of Window	Missing
Baseline	7 days before end of window	Last day that a daily TSS was collected between Day -7 and Day -1 (inclusive)	4 or more missing of the 7 daily TSSs in the window
Week 12	First day a daily TSS was collected between Day 78 and Day 84 (inclusive)	7 days after start of window	4 or more missing of the 7 daily TSSs in the window
Week 24	7 days before end of window	The day before the Week 24 visit	4 or more missing of the 7 daily TSSs in the window

7.4.2.1.2. Myelofibrosis Symptom Assessment Form v4.0 Total Symptom Score for Time-To-Event Endpoints

The MFSAF v4.0 TSS for baseline will be derived the same way as in Section 7.4.2.1.1. The daily postbaseline TSS will be calculated from Day 7 to the day before the Week 24 visit. The Day X TSS is the average TSS between Day X - 6 and Day X. For example, the TSS on Day 7 is the average of the TSS from Day 1 to Day 7. The missing individual score and the missing daily TSS will follow the rule defined in Section 7.4.2.

7.4.2.2. Proportion of Participants With a $\geq 50\%$ Reduction in Myelofibrosis Symptom Assessment Form v4.0 Total Symptom Score

The difference between the parsaclisib plus ruxolitinib group and the placebo plus ruxolitinib group in the proportion of participants who have a $\geq 50\%$ reduction in TSS from baseline to Week 24 evaluated by MFSAF v4.0 will be assessed using the CMH test stratified by baseline (or screening, if applicable) platelet count and DIPSS category at randomization for the ITT population as primary analysis and the PP population as sensitivity analysis. In the case that there is an insufficient number of participants enrolled in any DIPSS level within a platelet category, the collapsing rule specified in Section 7.1 will be applied. Missing values will not be imputed.

The percentage change from baseline to Week 24 will be calculated using the following formula:

$$\% \text{ change} = 100 \times (\text{Week 24 total score} - \text{baseline total score}) / \text{baseline total score}.$$

A participant will be considered as having achieved $\geq 50\%$ reduction of the TSS from baseline to Week 24 if the participant had both baseline and Week 24 TSSs, the participant did not make an early crossover to receive parsaclisib plus ruxolitinib prior to the Week 24 visit, and the percentage change from baseline was not missing and was less than or equal to -50% .

A participant who has a missing Week 24 TSS, discontinues treatment before Week 24, is unblinded prior to Week 24 for early crossover to parsaclisib plus ruxolitinib, or has a baseline value of 0 will be considered as having not achieved the $\geq 50\%$ reduction.

A participant who has a missing TSS baseline assessment will be considered as nonevaluable.

At the time of interim analysis, a participant who is still on treatment but has no timepoint assessment for TSS will also be considered as nonevaluable.

7.4.2.3. Mean Change and Percentage Change in Myelofibrosis Symptom Assessment Form v4.0 Total Symptom Score

The mean change and percentage change from baseline to Week X will be calculated using the following formula:

$$\% \text{ change} = 100 \times (\text{Week X total score} - \text{baseline total score}) / \text{baseline total score}.$$

The mean change and percentage change in TSS, the 7 individual scores, and the total score of the 3 spleen-related symptoms (including abdominal discomfort, pain under left ribs, and early satiety) from baseline to Week X will be summarized descriptively by treatment group and every 4 weeks using the ITT population. Missing values will not be imputed.

A plot of percentage change from baseline in MFSAF TSS at each visit will be provided.

7.4.2.4. Time to the First $\geq 50\%$ Reduction in Myelofibrosis Symptom Assessment Form v4.0 Total Symptom Score

The time to the first $\geq 50\%$ reduction in TSS is defined as the time from randomization to the first time participants have a $\geq 50\%$ reduction in TSS. The daily TSS will be calculated according to the algorithm defined in Section 7.4.2.1.2. Participants with valid, calculated baseline TSS and at least 1 postbaseline TSS who do not have $\geq 50\%$ reduction in TSS at the time of analysis will be censored at the time of the last valid calculated TSS. If the participants have no valid, calculated baseline or postbaseline TSS, they will be censored at the date of randomization.

The stratified log-rank test will be used to compare time to the first $\geq 50\%$ reduction in TSS between the 2 treatment groups in the ITT population at a 1-sided 2.5% significance level, stratified for baseline (or screening, if applicable) platelet count and DIPSS category. The strata identified in the randomization process will be used for the analysis.

Kaplan-Meier curves for the time to the first $\geq 50\%$ reduction in TSS will be presented by treatment group. The KM estimate of median time to the first $\geq 50\%$ reduction in TSS will be presented with its 95% CI. The 95% CI will be calculated using the generalization of method of Brookmeyer and Crowley (1982) with log-log transformation (Klein and Moeschberger 1997).

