2.2. Study Objectives and Endpoints

[Table 1](#) presents the objectives and endpoints.

Table 1: Objectives and Endpoints

Objectives	Endpoints
Primary	
To evaluate and compare the efficacy of parsaclisib plus ruxolitinib versus placebo plus ruxolitinib on spleen volume at Week 24. ^a	Proportion of participants achieving $\geq 25\%$ reduction in spleen volume from baseline to Week 24 as measured by MRI (or CT scan in applicable participants).
Secondary	
To evaluate and compare the effect of parsaclisib plus ruxolitinib versus placebo plus ruxolitinib on participant reports of MF symptoms. ^{b,c}	Proportion of participants who have a $\geq 50\%$ reduction in TSS from baseline to Week 24 as measured by the MFSAF v4.0 diary. Change in TSS from baseline to Week 24 as measured by the MFSAF v4.0 diary. Time to the first $\geq 50\%$ reduction in TSS as measured by the MFSAF v4.0 diary.
To evaluate and compare the effect of parsaclisib plus ruxolitinib versus placebo plus ruxolitinib with respect to OS. ^d	OS determined from the date of randomization until death due to any cause.
To evaluate and compare the safety and tolerability of parsaclisib plus ruxolitinib versus placebo plus ruxolitinib.	Safety and tolerability will be assessed by monitoring the frequency and severity of AEs, performing physical examinations, and evaluating changes in vital signs, ECGs, and laboratory results.
To evaluate and compare the time to onset and duration of response in spleen volume of participants receiving parsaclisib plus ruxolitinib versus placebo plus ruxolitinib. ^e	Time to the first $\geq 25\%$ reduction in spleen volume and duration of maintenance of a $\geq 25\%$ reduction in spleen volume.

Table 1: Objectives and Endpoints (Continued)

Objectives	Endpoints
Exploratory	

Table 1: Objectives and Endpoints (Continued)

Objectives	Endpoints
Exploratory (continued)	

^a Hypothesis 1: Proportions of participants achieving $\geq 25\%$ reduction in spleen volume from baseline to Week 24 in the 2 treatment groups are different.

^b Hypothesis 2: Proportions of participants achieving $\geq 50\%$ reduction in TSS from baseline to Week 24 as measured by the MFSAF v4.0 diary in the 2 treatment groups are different.

^c Hypothesis 3: Time to the first $\geq 50\%$ reduction in TSS as measured by the MFSAF v4.0 diary in the 2 treatment groups are different.

[figure not shown]
^d Hypothesis 4: The OS in the 2 treatment groups are different.

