3.2. Control of Type I Error

This study defines a single primary endpoint with a single primary analysis. The study will be claimed to have achieved the primary efficacy objective when the primary endpoint shows a significant result at 2-sided alpha of 0.05 at final analysis. The key secondary efficacy endpoints will be alpha-controlled and will be analyzed only when the study has reached the efficacy objective in the primary endpoint. The key secondary efficacy variables will be tested following a fixed-sequence-testing procedure with each at the 2-sided alpha level of 0.05 in the order below. Overall survival will be tested only if MFSAF TSS is significant.

1. The proportion of participants who have a $\geq 50\%$ reduction from baseline to Week 24 in the MFSAF TSS
2. OS

Descriptive statistics will be provided for other secondary [REDACTED] endpoints.

There will be 2 planned, nonbinding, futility analyses for this study based on the first 30% of participants enrolled in the study reaching Week 12 and Week 24 assessments of spleen volume and MFSAF TSS or discontinuing from treatment. As no formal decision for efficacy will be made based on these interim analyses, no overall alpha will be spent.

An independent DMC will be assembled to monitor safety data, efficacy data, and study conduct on a regular and ongoing basis during the study. See Section 10 for details regarding the alpha-spending plan and interim analyses conducted in this study.

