4.2 Secondary Efficacy	
4.2.2	Kaplan-Meier Estimates of Time to the First $\geq 50\%$ Reduction in MFSAF v4.0 Total Symptom Score
4.2.5	Plot of Percentage Change From Baseline in MFSAF v4.0 Total Symptom Score at Each Visit

Figure No.	Title

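### Time to first TSS response has its own 1-sided 2.5% significance test in SAP Section 7.4.2.4, although Section 3.2 leaves it outside the fixed sequence and makes it descriptive

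*SAP*

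**What the plan says.** Section 3.2 sets the confirmatory framework. The primary objective is met when the "primary endpoint shows a significant result at 2-sided alpha of 0.05 at final analysis". The key secondary endpoints are then "tested following a fixed-sequence-testing procedure with each at the 2-sided alpha level of 0.05 in the order below": first the Week 24 TSS responder rate, then OS ("Overall survival will be tested only if MFSAF TSS is significant"). For everything else the section says "Descriptive statistics will be provided for other secondary" endpoints. A word or two is blacked out in that sentence, but its application to the remaining secondary endpoints is legible. Time to first TSS response is not in the sequence.

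Three other places treat the same endpoint as a formal test:

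- **Table 1, Hypothesis 3** gives it a hypothesis, that the times to first "reduction in TSS as measured by the MFSAF v4.0 diary in the 2 treatment groups are different".
- **Table 2 (Section 5.3)** lists a stratified log-rank test for it under the label Inference, in the ITT population, with status P (preplanned).
- **Section 7.4.2.4** prescribes that test "between the 2 treatment groups in the ITT population at a 1-sided 2.5% significance level". It sets no condition on the primary result and does not call the p-value nominal.

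On early termination, the text closing Table 2 keeps preplanned analyses but drops time-to-event analyses with too few events. Sections 7.4.1.1 (time to first spleen response) and 7.4.3 (OS) each say that their analysis will not be performed. Section 7.4.2.4 has no such sentence. Appendix A still lists Table 2.2.2.3 and Figure 4.2.2 ("Kaplan-Meier Estimates of Time to the First" TSS response).

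**The concern.** A test with a hypothesis, an inference label and a significance level is not a descriptive statistic. Section 3.2 therefore cannot be followed together with Section 7.4.2.4 and Table 2. A report author working from Section 7.4.2.4 would compare the p-value with 2.5% and state whether the result is significant. One working from Section 3.2 would not.

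The fixed sequence exists so that no secondary result is called significant after the primary has failed. As written, Section 7.4.2.4 would allow exactly that for this endpoint.

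The point is live because the spleen time-to-response test, which has identical wording, and the OS test are both expressly cancelled and this one is not. It is the only time-to-event efficacy comparison in the visible text that still carries a significance level.

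There is also a mismatch of direction. A 1-sided test cannot declare a difference in favour of placebo, whereas Hypothesis 3 is non-directional.

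**Working it through.** **Inputs**
- Primary: 2-sided 0.05 (Section 3.2).
- Sequence after the primary: TSS responder rate, then OS, each 2-sided 0.05 (Section 3.2).
- Time to first TSS response: 1-sided 0.025, outside the sequence (Section 7.4.2.4). The section does not name the direction; I take it to favour parsaclisib.
- Correlation between test statistics: not in the SAP, so assumed.

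**Step 1. Is the per-test threshold looser?**
The critical value for 1-sided 0.025 is 1.960, and for 2-sided 0.05 it is also 1.960. This agrees with the final-analysis boundary in Tables 7 and 8 (Z > 1.96, one-sided p < 0.025). The threshold is not looser, and the error of this single test is 2.5%.

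**Step 2. Error of the sequence alone.**
Under the global null, the sequence can yield a false claim only if the primary rejects. Its familywise error is therefore 0.05 in either direction, or 0.025 counting only errors that favour parsaclisib.

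**Step 3. Add the extra test, supposing significance is declared on it (global null).**

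| Error counted | Sequence alone | With the extra test, independent | With the extra test, correlation 0.5 |
|---|---|---|---|
| False favourable claim (primary or this test) | 2.5% | 1 − 0.975 × 0.975 = 0.0494 | 0.0454 |
| Any false claim (primary in either direction, or this test) | 5% | 1 − 0.95 × 0.975 = 0.0738 | 0.0704 |

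Whatever the correlation, the additive (Bonferroni) bounds are 0.025 + 0.025 = 0.05 and 0.05 + 0.025 = 0.075.

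**Step 4. A real spleen effect but no TSS effect.**
The primary now passes, and the two null tests are the TSS responder rate (2-sided 0.05) and time to first TSS response (1-sided 0.025). Both come from the same diary, so a positive correlation is likely. By simulation with 2 million draws:

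| Assumed correlation | Any false TSS claim | False favourable TSS claim |
|---|---|---|
| 0 | 0.0737 | 0.0494 |
| 0.5 | 0.0702 | 0.0453 |
| 0.9 | 0.0602 | 0.0353 |

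**Step 5. After the correction.**
If the p-value is nominal and supports no claim, familywise error over the confirmatory claims stays at 5% (2-sided).

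**The case against.** The strongest reply is that Section 3.2 is where the SAP governs claims, and it already excludes this endpoint. A reader might infer from Section 7.4.2.4 that the sponsor plans a secondary claim with no type I error control. The documents do not support that. No passage says a claim will rest on this test, and the test has its own 2.5% error rate. Only familywise control is missing, and only if significance is declared. Every figure in Step 3 and Step 4 carries that condition.

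A reader might also infer that the 1-sided level departs from a 2-sided convention used everywhere else. It does not: Tables 7 and 8 state the final boundary as one-sided 0.025, and Section 7.4.1.1 uses the same wording. The mismatch is with Section 3.2 and Hypothesis 3, and it is one of notation and direction, not of stringency. Likewise, an inflation to 9.75% (1 − 0.95 × 0.95) would describe an independent 2-sided 5% test, which Section 7.4.2.4 does not plan.

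The practical stakes are limited too. The study ended early and OS will not be analysed. The rule on too few events could yet drop this test, and Appendix A is weak evidence that it will be run: Figure 4.2.2 is estimation only, and the title of Table 2.2.2.3 names no test, unlike the responder tables, which name the CMH test.

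These points narrow the concern but do not remove it. Section 3.2 does not clearly override Section 7.4.2.4, which is the more specific text, and nothing in the SAP applies the rule on too few events to this endpoint.

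**Conclusion.** The SAP contradicts itself on the status of time to first TSS response: descriptive in Section 3.2, but formally tested in Table 1, Table 2 and Section 7.4.2.4. The test lies outside the fixed sequence, does not depend on the primary result and has not been cancelled.

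If significance were declared on it, the chance of a false favourable claim under the global null would go from 2.5% to about 4.9%, and of any false claim from 5% to about 7.4%. Both figures assume independence; at a correlation of 0.5 they are 4.5% and 7.0%. These sizes describe what the wording permits, not a claim that the SAP announces.

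The primary analysis and the Section 3.2 sequence are unaffected. The correction is still worth making, because it settles what may be concluded from a comparison that may still be reported.

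**What to change.** 1. In Section 7.4.2.4, delete the clause that sets the 1-sided 2.5% level, and add a sentence such as: *The stratified log-rank p-value is two-sided and nominal and supports no claim of statistical significance.*
2. In Table 2, relabel the log-rank entry for this endpoint so that it no longer reads as confirmatory inference.
3. In Table 1, mark Hypothesis 3 as outside the confirmatory tests, in line with Section 3.2.

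The Section 3.2 sequence needs no change. Section 7.4.1.1 carries the same clause but needs only tidying, because that analysis is cancelled.

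The cost is a few words in three places, with no new data or analysis. The sponsor gives up a stand-alone significance statement for this endpoint.
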